**List of Abbreviations**

In the following abbreviations are listed as used within this statistical analysis plan or which might occur within the tables, listings and graphs outputs:

AE	Adverse event
ATC	Anatomical therapeutic chemical classification
BMI	Body mass index
CCS	Carolinas comfort scale™
CDC	US centers for disease control and prevention
CI	Confidence interval
Cm	centimeter
COPD	Chronic obstructive pulmonary disease
CS	Clinically significant
CST	Component separation technique
CT	Computed tomography
eCRF	Electronic case report form
EoS	End of study
ET	Early termination
FU	Follow-up
ICF	Informed consent form
ITT	Intention-to-treat
MCS	Mental component summary
MedDRA	Medical dictionary for regulatory activities
mITT	modified intention-to-treat
MRI	Magnetic resonance imaging
MSE	Missing score estimation
N	Number of subjects
NA	Not applicable
NCS	Not clinically significant
OP	Operation
OTC	Over the counter
PCS	Physical component summary
PP	Per-protocol
PT	Preferred term
SAE	Serious adverse event
SAP	Statistical analysis plan
SD	Standard deviation
SOC	System organ class
SF-12®	12-item short form
SSI	Surgical site infection
TLG	Tables, listings, graphs
UV	Unscheduled visit
V	Version
VAS	Visual analog scale
WHO-DD	World health organization drug dictionary

## 1 General

This Statistical Analysis Plan (SAP) was defined by the Sponsor and the responsible Statistician. It is based upon the Study Protocol (version 4.0 of October 30, 2017) and contains detailed description of the statistical methods described therein.

The SAP describes prospectively the analyses to be performed on study data. It was finalized prior to data base lock.

This is a post-market, prospective, multi-center, open-label study designed to collect additional data on safety, performance and effectiveness of Phasix™ Mesh for primary ventral or incisional or multiply-recurrent hernia repair in subjects with a higher level of risk. Subjects at high risk are defined as having one or more of the following co-morbidity conditions: body mass index (BMI) between 30-40 kg/m^2, active smokers, chronic obstructive pulmonary disease (COPD), diabetes mellitus, immunosuppression, coronary artery disease, chronic corticosteroid use, serum albumin less than 3.4 g/dL, advanced age or renal insufficiency. Subjects who receive a Phasix™ Mesh implant will be followed for 60 months with follow-up visits conducted at 1, 3, 6, 12, 18, 24, 30, 36, 42, 48, 54 and 60 months following surgery. At the 30, 42 and 54 month visit a telephone contact should be scheduled with the subject. If the investigator determines the responses provided by the subject demands a physical examination be conducted, a clinic visit will be scheduled.

This clinical study is projected to enroll up to 120 subjects at approximately 16 US sites. The sample size of 120 subjects is based on potential adequacy of data to meet the study objectives. No formal sample size calculation was performed.

The two primary endpoints are hernia recurrence rate and surgical site infection (SSI) rate. There is no formal statistical hypothesis for this post-market study with a single treatment condition.

## 2 Primary and Secondary Variables

### 2.1 Primary Variables

The two primary parameters for this study are:

- Hernia recurrence rate
- Surgical site infection (SSI) rate

### 2.2 Secondary Variables

The following secondary parameters will be analyzed:

- Pain - Visual Analog Scale (VAS)
- Device related adverse event incidence
- Rate of reoperation due to the index hernia repair
- Quality of life assessments (Carolinas Comfort Scale™ and SF-12® - 12-item short form health survey)
- Surgical procedure time as measured from incision to closure (skin to skin)
- Length of stay

### 2.3 Safety Variables

- Physical examination
- Adverse events (AEs)
- Device failure, malfunctions and defects
- Concomitant pain medication

### 2.4 Other Relevant Variables

- Protocol deviations

### 3 Statistical Analysis Sets

#### 3.1 Intention-to-treat Set

The intention-to-treat (ITT) set consists of all enrolled subjects who have signed the informed consent form (ICF).

#### 3.2 Modified Intention-to-treat Set

The modified ITT (mITT) set is defined as those subjects in the ITT set in whom Phasix™ Mesh has been implanted.

#### 3.3 Per-protocol Set

All subjects of the mITT will also be included in a per-protocol (PP) set if they do not violate any major protocol criteria. Protocol deviations will be identified and classified for each subject during a data review (see section 4.8).

The violation of any inclusion or exclusion criterion is a priori defined to have a “major” grade and will lead to an exclusion from the PP set. If for a subject the Phasix™ Mesh was cut through or a piece of the Phasix™ Mesh was removed during a surgery not related to the index hernia repair, the subject will be excluded from the PP set as well. The inclusion and exclusion criteria as defined in the latest protocol version will be decisive irrespective which protocol version at time of subject’s enrollment was effective or if a new protocol version was approved by the site.

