#### 3.5 Assignment of Analysis Sets to Analysis

The mITT set will be considered the primary analysis. All analyses are based on the mITT set. In-/ exclusion criteria (where applicable with reason for failure to meet eligibility criteria), subjects per study site, applicable protocol version and demographics (listing only) will be presented for the ITT set. Adverse events of subjects in the ITT set but not in the mITT set

will be listed as well. The primary and secondary variables will additionally be analyzed using the PP set (including the subgroup analyses by gender but no further subgroup analyses).

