### **4.8 Data Base Closure and Data Review**

A data base closure will be performed prior to the analysis. All parameters will be checked, as specified in the data validation plan, and all queries resolved before data base closure and analysis.

A data review will be conducted prior to data base closure to check for protocol deviations and to allocate the subjects to the analysis sets. At least the following items will be discussed:

- Informed consent form signed (date subject signed informed consent is documented)
- Phasix™ Mesh implantation
- Any violation of inclusion/exclusion criteria
- Subjects for which the index hernia repair/ Phasix™ Mesh was cut through or a piece of the Phasix™ Mesh was removed during a surgery not related to the index hernia repair (for example documented as other action taken on the AE form)
- Reasons for premature discontinuation
- Protocol deviations as captured in the eCRF on the protocol deviation log page

If required, critical data/ analysis issues can additionally be discussed (e.g. review reasons for reoperations, SSIs and hernia recurrences).

These evaluations and assessments will be done together and in agreement with the Sponsor, however FGK will provide the Sponsor with the appropriate subject listings (as defined in Appendix A to the SAP). Data review can be done via a telephone conference or in writing.

After data review minutes (including the affiliation of subjects to the ITT, mITT and the PP set) have been signed by both the Sponsor and FGK, data base closure will be performed.

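### A later unrelated operation removes a subject from the per-protocol set from day 0, so PP membership depends on a future event and valid earlier data drop out of the PP analyses

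*SAP*

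**What the plan says.** SAP 3.2 defines the mITT set as "those subjects in the ITT set in whom Phasix™ Mesh has been implanted", and SAP 3.5 states: "The mITT set will be considered the primary analysis". The PP set is the supportive set: "The primary and secondary variables will additionally be analyzed using the PP set".

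SAP 3.3 gives two routes out of the PP set. The first is violation of any inclusion or exclusion criterion, graded major in advance. The second applies if the mesh was cut through or partly removed in an operation unrelated to the index repair: "the subject will be excluded from the PP set as well". No date limit is attached.

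The rule is applied in retrospect. SAP 4.8 states: "A data review will be conducted prior to data base closure to check for protocol deviations and to allocate the subjects to the analysis sets". One review item covers subjects whose repair or mesh was cut through, or in whom a piece of mesh "was removed during a surgery not related to the index hernia repair". The example source given is "for example documented as other action taken on the AE form".

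The Kaplan-Meier censoring rule in SAP 4.4.1 names completion, discontinuation, or last visit for subjects lost to follow-up. It does not name an unrelated operation.

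**The concern.** Cutting or removing part of an implanted mesh can happen only after implantation, at any point in up to 60 months. Until it happens, the subject's data meet the protocol as well as anyone else's. The rule nevertheless removes the subject from day 0. Longer follow-up also gives more opportunity to be removed.

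The loss reaches every endpoint repeated in the PP set: recurrence, SSI, reoperation, patient-reported outcomes, procedure time and index length of stay. The last two are settled around the index operation and cannot be altered by surgery years later.

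What is at stake is the use of the PP result as a check on mITT. A difference between the two that arises from this rule says nothing about protocol adherence. No planned analysis uses these subjects only up to the operation: PP drops all their data, and mITT keeps all of it, including follow-up after the mesh was cut.

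**Working it through.** The documents give no figure to reproduce. There is no hypothesis (Protocol 7.1), the sample size has no statistical basis (Protocol 7.2), and no expected recurrence rate or number of such operations is stated. The counts and risks below are therefore assumptions.

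**1. Data lost per subject.** In the SAP section 4 interval table, the first eleven intervals end at visit day plus window: days 37, 120, 210, 395, 575, 760, 940, 1125, 1305, 1490 and 1670. An operation on day 1300 comes after 8 completed intervals (the eighth ends on day 1125). One on day 1700 comes after 11. All of these leave the PP set.

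**2. Effect on a crude rate.** Assume 120 implanted and 18 recurrences: 18/120 = 15.0% (exact 95% CI 9.1 to 22.7). If m subjects are excluded and r of them had recurred, the PP rate is (18 − r)/(120 − m).

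| m | r | PP rate | Exact 95% CI |
|---|---|---|---|
| 6 | 0 | 18/114 = 15.8% | 9.6 to 23.8 |
| 6 | 1 | 17/114 = 14.9% | 8.9 to 22.8 |
| 6 | 6 | 12/114 = 10.5% | 5.6 to 17.7 |

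The extremes are 12.8% to 15.4% for m = 3 and 5.6% to 16.7% for m = 12. The row with r = 1 is close to independence (6 × 15% = 0.9 expected). There the rate barely moves, and the interval width goes from 13.6 to 13.9 points.

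**3. When the expected rate shifts.** Assume constant hazards over 5 years:
- 60-month recurrence risk 15%: λ = −ln(0.85)/5 = 0.0325 per year.
- 60-month cut-through risk 10% before recurrence: μ = −ln(0.90)/5 = 0.0211 per year.
- h = cut-through hazard after recurrence divided by that before it.

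P(no recurrence and still in PP) = 0.85 × 0.90 = 0.765.

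P(recurrence and still in PP) = a(h) = ∫₀⁵ λ·exp(−λt)·exp(−μt)·exp(−hμ(5 − t)) dt.

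PP rate = a/(a + 0.765).

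| h | a(h) | PP rate, whole-subject exclusion |
|---|---|---|
| 0 | 0.1426 | 15.7% |
| 1 | 0.90 × 0.15 = 0.1350 | 15.0% |
| 3 | 0.1214 | 13.7% |
| 5 | 0.1095 | 12.5% |

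With recurrence risk from 10% to 20% and cut-through risk from 2.5% to 10%, the shift is +0.1 to +0.9 points at h = 0, none at h = 1, −0.2 to −1.7 at h = 3, and −0.5 to −3.2 at h = 5.

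**4. Ending follow-up at the operation.** In a simulation of 2,000,000 subjects under the 15% and 10% assumptions, the estimate censored at the operation was 15.0% for all four values of h. An affected subject had on average about 29 to 31 months of follow-up before the operation, all of it dropped under the present rule.

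**5. Why censoring alone is not enough.** The overall rate in SAP 4.4.1 is crude and ignores individual study duration. Counting only recurrences before the operation, with every subject in the denominator, gives λ/(λ + μ) × (1 − 0.765) = 0.1426, or 14.3% against a true 15.0%. The unobserved time would count as event-free.

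**The case against.** The strongest reply is that little depends on this. mITT is primary and untouched, the analyses are descriptive with no hypothesis, and Protocol 7.3 treats the PP set as optional. Every observation from these subjects stays in mITT. The rule is openly stated, and the revision history records it as added in SAP version 3.0. Protocol 5.3.2 uses much the same event to bar entry to the extension. Whole-subject exclusion could be defended as a choice of estimand. The number affected may be zero.

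Most of this stands, and it limits the point to the supportive analysis. A reader might infer that the trial's main result is compromised, or that the PP rate is biased in a known direction. The documents support neither. Bias needs an association between the operation and the endpoint, and nothing in the documents establishes one. For procedure time and length of stay, only a smaller sample has been shown.

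A reader might also conclude that only violations present at or before implantation should exclude. That would conflict with Protocol 7.3, which removes subjects for any major deviation whenever it occurs.

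The defence does not remove the conditioning on a future event. Stating a rule in advance makes it transparent, but the data before the operation were still collected as planned.

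**Conclusion.** The point holds for the PP set only. SAP 3.3 makes membership depend on a post-implant event and drops valid earlier data from all PP primary and secondary analyses.

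The size cannot be fixed from the documents. With 6 of 120 excluded and 18 recurrences, the PP rate could be anywhere from 10.5% to 15.8% against 15.0%. Under independence the expected shift is zero and the cost is precision. Under the modelled associations the shift runs from +0.9 to −3.2 points. These figures rest on assumed counts, constant hazards and all 120 subjects being implanted. The change is worth making because it is cheap and lets the PP result be read as a check on mITT, but no primary conclusion depends on it.

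**What to change.** For this one criterion, amend SAP 3.3 to keep the subject in the PP set and end PP follow-up at the date of the unrelated operation:

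- **Kaplan-Meier (SAP 4.4.1, recurrence and SSI):** events before that date count, and event-free subjects are censored there. State how an event dated on the operation day is handled.
- **Interval tables (recurrence, SSI, reoperation):** treat the date like a discontinuation date, so an interval not completed by then leaves the denominator unless an event occurred first.
- **Overall PP rates:** take cumulative recurrence and SSI from Kaplan-Meier, or label the crude rate as not allowing for shortened follow-up.
- **Patient-reported outcomes:** omit scores after that date.
- **Procedure time and index length of stay:** keep in full.
- **Other exclusions:** leave eligibility violations and other major deviations as in Protocol 7.3 and SAP 3.3. A subject entered into the extension in breach of Protocol 5.3.2 therefore still leaves the PP set.

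The cost is SAP wording and modest extra programming, with no new visits. The sponsor must confirm that the operation date is recorded, since SAP 4.8 cites only an adverse event form entry as an example source. Censoring also assumes that the operation is non-informative about later recurrence or infection, and the SAP should say so.

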#### 3.4 Additional subgroup analysis

Where appropriate, subgroup analysis (based on the mITT set) may be performed for the two primary parameters if enough subjects within the subgroups allow further insight to the data. Following subgroups are subject to further interest:

- ❑ Gender: Male versus female subjects
- ❑ Centers: Study sites with  $\leq 5$  subjects in the mITT set will be combined to one site.
- ❑ Pre-operative diagnosis: ‘Primary ventral or incisional hernia’ versus ‘recurrent ventral or incisional hernia’ (regardless of first-recurrent or multiple-recurrent hernia) versus ‘Other’ (if applicable). Other pre-operative diagnoses, which are multiple recurrences as documented on the protocol deviation form, will be allocated to the subgroup ‘recurrent ventral or incisional hernia’ and not kept in subgroup ‘Other’.
- ❑ Surgical procedure performed with ‘Retro-rectus with CST’, ‘Retro-rectus without CST’, ‘Onlay placement with CST’, ‘Onlay placement without CST’ and ‘Other’.

The ‘by gender’ analysis will be performed for all primary and secondary parameters and for the analysis of procedure related AEs by time intervals.

The subgroups of ‘Surgical procedure performed’ will additionally be considered in the analyses of device and procedure related AEs by time intervals.

#### 3.5 Assignment of Analysis Sets to Analysis

The mITT set will be considered the primary analysis. All analyses are based on the mITT set. In-/ exclusion criteria (where applicable with reason for failure to meet eligibility criteria), subjects per study site, applicable protocol version and demographics (listing only) will be presented for the ITT set. Adverse events of subjects in the ITT set but not in the mITT set

will be listed as well. The primary and secondary variables will additionally be analyzed using the PP set (including the subgroup analyses by gender but no further subgroup analyses).

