#### 6.1.3 Eligibility

The subject's eligibility for study enrollment will be reviewed and documented on the appropriate eCRF. At the time of screening, a related progress note must be entered in the source documentation to indicate that all eligibility criteria were reviewed and screening results noted. Final eligibility will be determined intraoperatively.

Subjects who fail to meet eligibility criteria should be considered screen failures and treated according to the Investigator's standard of care. Data are to be collected for screen failure subjects from the time the ICF is signed until the subject is deemed a failure. At a minimum, subject demographics and the reason for failure must be collected; adverse events (AEs) will also be collected and followed through satisfactory resolution or stabilization.

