#### 6.3 Subject Follow-up

#### 6.3.1 Subjects Not Implanted and Surgical Repair Failures

Subjects who are screened but do not have the test device placed should be considered a screen failure and treated per hospital standard of care. Screen failure subjects who experience a protocol defined AE will be followed through satisfactory resolution or stabilization of the event.

Reason for failure of the surgical repair procedure, as well as all information outlined in Section 6.2.3 must be recorded in the source documentation.

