# 9 MECHANICAL FAILURES, MALFUNCTIONS AND DEFECTS

The Investigator will record if the surgical mesh device used in the study procedure failed to meet its performance specifications whether due to mechanical failure, malfunction or defects. This applies to: devices used in the subject, devices in which the package was opened but the device was not used for implantation in the subject, or devices with which implantation was attempted, but the device did not remain (was not used) in the subject.

A recurrence (unless it is in a different location than the study hernia) is considered a device failure if the recurrence is clearly device related, and not procedure related or an issue of patient mismanagement (e.g., use of a Vacuum Assisted Closure (VAC) system for too long; mesh used was too small to adequately cover the defect), as determined by the Investigator.

All mechanical failures, malfunctions, missing components, foreign matter inclusion or any other defects of the study device or any components of the device kit that do not perform to specifications must be promptly reported to the Davol Field Assurance Department:

Field Assurance Department e-mail: [contact]

[contact] [name] – [name] e-mail: [contact]

The event must also be documented on the Device Failure eCRF and the malfunctioning device promptly returned to the manufacturer.

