#### Device failure, malfunctions and defects

The investigator records if the surgical mesh device used in the study procedure failed to meet its performance specifications whether due to mechanical failure, malfunction or defects. Device failure, malfunctions or defects will be tabulated by the failure code.

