#### 4.9 Miscellaneous

For qualitative variables the frequencies (absolute and relative) are calculated. If no further remark is given in the description of the tables following format will be used for all tables with qualitative variables:

	Y-variable(s) (e.g., subgroups)					
	Category 1		Category 2		Total	
X-variable(s)	N	%	N	%	N	%
category 1						
category 2						
missing						
Total		100.0		100.0		100.0

For this standard format the description of the tables in Appendix A determines only the X- and Y-variables. If another format of table is described in the details to the tables, the real design will be determined by the technical possibilities within SAS and may not look identical to the provided example. However, all information as displayed will be included.

Quantitative parameters will be described by declaring the number of non-missing values (N), number of missing values (missing), mean value (mean), standard deviation (SD), minimum, 1st quartile, median, 3rd quartile, and maximum. In the description of the tables this will be denoted by „basic statistics“.

If not stated differently, in the presentation of frequency tables special missing values, as ‘not done’, ‘unknown’, ‘not applicable’, ‘not documented’, will be presented separately as far as they occur. In tables with “basic statistics” they will be merged to ‘missing’. In the listings they will be displayed as captured in the eCRF.

The listings are always sorted by center and subject. All listings with information about several visits will be sorted by center, subject and visit date so that unscheduled visits are

displayed in chronological order according to the visit dates. If a different sorting order should be used for some listings this will be remarked separately. The variables for the special listings are explicitly given in the description of listings. All listings will be presented for the mITT set, if not stated differently.

Subjects enrolled but without Phasix™ Mesh implantation (e.g. withdrawal before implantation) will be considered in tables and listing describing subjects per analysis set, per study site, per applicable protocol version and inclusion/ exclusion criteria as well as in listings for subject demographics and adverse events.

The following title will be used for all generated tables, listings, and graphs:

DVL-HE-011: Phasix™ Mesh

Page # of #

---

<Subtitle for description of contents - if applicable>

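### A device failure that leaves a subject with no Phasix mesh must be recorded under Protocol 9 but reaches no output named in the body of the SAP

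*SAP*

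**What the plan says.** Protocol 9 defines failure recording by device. It covers meshes used in the subject, meshes whose package was opened without being used for implantation, and "devices with which implantation was attempted, but the device did not remain (was not used) in the subject". Each event goes on the Device Failure eCRF and is reported to the sponsor's field assurance department.

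SAP 2.3 names device failure, malfunctions and defects as a safety variable. SAP 4.5 gives the analysis in one sentence: "Device failure, malfunctions or defects will be tabulated by the failure code". It names no analysis set, so the general rule in SAP 3.5 applies: "All analyses are based on the mITT set". SAP 3.2 defines that set as "those subjects in the ITT set in whom Phasix™ Mesh has been implanted".

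SAP 3.5 makes exceptions for eligibility criteria, subjects per site, protocol version and a demographics listing, all shown for the ITT set. It adds a listing for "Adverse events of subjects in the ITT set but not in the mITT set". SAP 4.9 repeats where non-implanted subjects appear: tables and listings on analysis set, site, protocol version and eligibility, "as well as in listings for subject demographics and adverse events". It also makes mITT the default for listings unless stated otherwise.

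For subjects without an implant, Protocol 7.3 provides for a separate summary of AEs and no collection or analysis of outcome data.

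**The concern.** The protocol deliberately records failures of meshes that never stayed in a patient. The SAP then analyses device failures in a set defined by the mesh having been implanted. Where the failure is itself the reason that no mesh was implanted, the event removes the subject from the set in which it would have been counted.

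The stake is the completeness of a named safety variable. A reader of the final tables would take the device-failure table to cover everything Protocol 9 asked sites to record, and would not know that this kind of failure had been left out.

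A smaller mismatch concerns device-related AEs, a secondary endpoint. The protocol promises a separate summary of AEs in non-implanted subjects. The SAP only lists them, and SAP 5 (Changes from Protocol) does not mention the difference.

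**Working it through.** The documents state no device-failure rate, so there is no figure to reproduce. The check traces the set rules and then gives an illustration.

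**Tracing one failure through the rules**

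1. A mesh fails on opening or during attempted implantation. Protocol 9 requires it to be recorded on the Device Failure eCRF.
2. Case A: another Phasix mesh is implanted. The subject meets SAP 3.2 and is in mITT, and the failure enters the SAP 4.5 table.
3. Case B: no Phasix mesh is implanted. Protocol 6.3.1 applies: "Subjects who are screened but do not have the test device placed should be considered a screen failure". The subject is in ITT but not in mITT.
4. In case B the SAP 4.5 table leaves the failure out, because SAP 3.5 sets mITT as the basis and SAP 4.5 names no other set.
5. A listing leaves it out as well, because SAP 4.9 defaults listings to mITT and does not name device failure among the outputs for non-implanted subjects.
6. Any AE that accompanied the failure appears in the separate AE listing, but not in the device-related AE incidence of SAP 4.4.2. A device failure without a clinical event is not an AE and would not appear there either.

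The gap is therefore confined to case B.

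**Illustration of size (assumed inputs)**

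The documents do not give the number of case B events. Assume 120 attempted implantations (the projected maximum enrolment in Protocol 5.1 and 7.2), k of them case B, and no other failures. The table population is 120 − k with 0 failures. The proportion of all attempts is k/120. Intervals are exact (Clopper-Pearson) two-sided 95%.

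| k | mITT table | All attempts |
|---|---|---|
| 1 | 0/119 = 0% (0 to 3.1%) | 1/120 = 0.8% (0.02 to 4.6%) |
| 2 | 0/118 = 0% (0 to 3.1%) | 2/120 = 1.7% (0.2 to 5.9%) |
| 3 | 0/117 = 0% (0 to 3.1%) | 3/120 = 2.5% (0.5 to 7.1%) |
| 5 | 0/115 = 0% (0 to 3.2%) | 5/120 = 4.2% (1.4 to 9.5%) |

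With two further failures among implanted subjects and k = 3, the table would show 2/117 = 1.7%, against (2 + 3)/120 = 5/120 = 4.2%. In counts, which is all SAP 4.5 promises, the table is short by exactly k.

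**The case against.** The other side has several good points.

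- **AEs are not lost.** A reader might infer from Protocol 6.1.3 ("Data are to be collected for screen failure subjects from the time the ICF is signed until the subject is deemed a failure") that AE collection stops in the operating room. The documents do not support this. The same section goes on to say that AEs are also collected and followed to resolution or stabilization. Protocol 6.3.1 repeats the follow-up for screen failures, and Protocol 8 collects AEs to the end of participation. Keeping these AEs out of an incidence among implanted subjects is a choice disclosed in Protocol 7.3. What remains is only that the protocol says summary and the SAP says listing.
- **No one-way bias in a rate is shown.** A reader might infer that the reported failure rate can only be too low. SAP 4.5 states no rate or denominator. A wider denominator would also admit subjects whose mesh was opened without failing and who were then excluded intraoperatively. With three of those, 2/117 = 1.71% becomes 2/120 = 1.67%, slightly lower. The supported statement is about omitted counts.
- **Replacement keeps most subjects in.** The mesh is commercial and comes in several sizes, so a failed one may simply be replaced. That is case A, and it narrows the gap without closing it.
- **Protocol 6.1.2 and 6.3.1 define screen failure differently.** The former requires failed eligibility as well as no device. This does not affect the result, because mITT membership depends on implantation alone.
- **Appendix A is unseen.** It specifies the tables and listings, and each output carries its own analysis-set line, so it could already assign another set. This stands as a limit on the finding.

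Individual reporting to the sponsor is also unaffected. The gap is in the analysis.

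**Conclusion.** The point holds in a narrow form. The SAP body provides no table or listing for a device failure in a subject who ends with no Phasix mesh, although Protocol 9 requires that failure to be recorded. The device-failure table would be short by the number of such events. That number is unknown and may be zero. The illustrated 0.8% to 4.2% rests on an assumed 1 to 5 events in 120 attempts with no other failures.

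The conclusion assumes that Appendix A does not name a wider set for this output. It also depends on how the sponsor classifies a mesh placed and then removed in the same operation, which the mITT definition leaves open. The primary endpoints are not affected, and the device-related AE incidence is properly kept on mITT. It is worth correcting because it concerns a named safety variable and the failure data are already collected.

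**What to change.** 1. In SAP 3.5, 4.5 and 4.9, add device failures, malfunctions and defects to the outputs shown beyond mITT. Present them for all ITT subjects with a Device Failure eCRF entry, as counts by failure code with separate rows for implanted and not implanted, and add a listing.
2. Give a rate on attempted implantations only if that number can be confirmed from surgical records. Protocol 12.5 does not require device accountability, so packages opened without a failure may not have been recorded.
3. Keep the device-related AE incidence in SAP 4.4.2 on mITT. Beside it, show the device-related AEs of non-implanted subjects as a separate count, which meets the separate summary foreseen in Protocol 7.3.
4. State in the SAP how a mesh placed and removed in the same operation is classified, so that the two rows are unambiguous.
5. Check Appendix A and align its analysis-set lines with these changes.

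The cost is SAP wording, one extra row, one listing and one AE count. The failure data are already on the eCRF. The failure count may look slightly less favourable. If no such events occurred, the new row shows zero and documents that fact.
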